6.3.1 Time to Subsequent Systemic Treatment

The endpoint, time to subsequent systemic treatment, will be defined as the time from start date of larotrectinib (for SCOUT) or start date of chemotherapy (for historical control cohorts) till the start

date of a post-treatment systemic anti-cancer therapy, if any. Patients who do not take a subsequent systemic treatment will be censored at the last known alive date.

6.3.2 Time to Mutilating Surgery including Limb Amputation

The endpoint, time to mutilating surgery including limb amputation, will be defined as the time from start date of larotrectinib (for SCOUT) or start date of chemotherapy (for historical control cohorts) till the start date of a mutilating surgery (including limb amputation), if any. Patients who do not record a mutilating surgery (including limb amputation) will be censored at the last known alive date.

6.3.3 Time to First Radiation Therapy

The endpoint, time to radiation therapy, will be defined as the time from start date of larotrectinib (for SCOUT) or start date of chemotherapy (for historical control cohorts) till the start date of a radiation therapy, if any. Patients who do not record a radiation therapy will be censored at the last known alive date.

6.3.4 Time to Complete Surgical Resection (excluding Amputation and Any Other Mutilating Surgeries)

The endpoint, time to complete surgical resection (excluding amputation and any other mutilating surgeries), will be defined as the time from start date of larotrectinib (for SCOUT) or start date of chemotherapy (for historical control cohorts) till the start date of a complete surgical resection (excluding amputation), if any. Patients who do not record a complete surgical resection (excluding amputation) will be censored at the last known alive date. Subject recording a R0 resection (no residual tumor) are considered to have achieved complete surgical resection. Additionally for this study, subjects recording a R1 surgery (macroscopic residual tumor) will also be included for complete surgical resection as there is no additional treatment in this case for IFS.

6.3.5 Overall Survival

OS is the time from start date of larotrectinib (for SCOUT) or start date of chemotherapy (for historical control cohorts) till time of death due to any cause. Patients alive at the time of analysis will be censored at the last known alive date.

6.3.6 Progression-Free Survival

PFS is the time from start date of larotrectinib (for SCOUT) or start date of chemotherapy (for historical control cohorts) till earlier of disease progression/relapse assessed by radiological or clinical examination or death due to any cause. Patients without an event at the time of analysis will be censored according to the rules contained within

Rules for Determining Date of Progression or Censoring for Progression-Free Survival

Rule	Situation	Date of Progression or Censoring	Outcome
1	No baseline tumor assessments	Date of First Larotrectinib Treatment or Chemotherapy	Censored
2	No post-baseline assessments and no death	Date of First Larotrectinib Treatment or Chemotherapy	Censored
3	No progression (clinical or radiological) and no death (with a post-baseline tumor assessment)	Date of last available tumor assessment	Censored
4	Patient lost to follow-up (or withdrew consent from study participation) prior to progression (clinical or radiological) or death	Date of last available tumor assessment	Censored
5	Progression (clinical or radiological)	Date of assessment where progression was confirmed	Progressed
6	Death without earlier progression	Date of death	Progressed
7	New anti-cancer therapy prior to progression (as assessed by medical expert)	Date of last tumor assessment before initiation of new therapy	Censored

6.3.7 Overall Response Rate

ORR is defined as the proportion of patients with a best overall response of CR or PR assessed by investigators.

Summary statistics for ORR with 95% 2-sided exact binomial confidence intervals will be reported. In addition, a weighted analysis will be conducted. The binary response outcome (ORR), is regressed on group indicator (larotrectinib, comparator) using a logistic regression model, incorporating the IPTW weights calculated for the primary endpoint. Standard errors are calculated using a robust sandwich estimator. The odds ratio comparing larotrectinib to comparator, with 95% confidence interval, will be provided. A corresponding odds ratio will also be reported for the unweighted samples.

6.3.8 Disease Control Rate

Disease control rate (DCR) is defined as the proportion of patients with a best overall response of CR or PR or SD as assessed by investigators.

Summary statistics for DCR with 95% 2-sided exact binomial confidence intervals will be reported. In addition, a weighted analysis will be conducted. The binary response outcome (DCR), is regressed on group indicator (larotrectinib, comparator) using a logistic regression model, incorporating the IPTW weights calculated for the primary endpoint. Standard errors are calculated using a robust sandwich estimator. The odds ratio comparing larotrectinib to comparator, with 95% confidence interval, will be provided. An odds ratio for the unweighted samples will also be reported.

6.4 Safety Analysis

Safety Analyses will be limited to calculating incidence of treatment discontinuation due to treatment-emergent adverse events (regardless of relatedness to treatment). This endpoint will be summarized descriptively by treatment group, with proportions and 95% 2-sided exact binomial confidence intervals, in the original unweighted sample only.

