8.2 Secondary objectives

The secondary objectives in this study include the comparison of:

- Treatment outcomes (next systemic treatment, mutilating surgery, radiation therapy, death due to any cause),
- Treatment discontinuation rates due to toxicity.

9. Research methods

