9.1.2 Secondary endpoints

The secondary endpoints of the study are:

- Time to subsequent systemic treatment.
- Time to mutilating surgery including limb amputation.

- Time to radiation therapy.
- Time to complete surgical resection (excluding amputation).
- OS, defined as the time (months) from the start of treatment to the date of death due to any cause. Patients alive or lost to follow-up at the time of analysis will be censored at their last date of follow-up.
- Incidence of patients with treatment discontinuation due to treatment-related adverse events (AEs).

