9.3.4 Potential confounders

The following baseline variables will be considered when balancing the two cohorts: IFS patients enrolled in SCOUT study and the external historical control cohort(s).

- Patients and disease characteristics:
 - Sex,
 - Age,
 - Disease history:
 - Date of initial diagnosis,
 - Anatomical disease site(s) at diagnosis,
 - Stage of disease at diagnosis (local versus locally advanced versus metastatic),
 - Primary tumor size (< 5 cm or > 5 cm),
 - Date of advanced disease stage evolution (locally advanced, metastatic),
 - Time from locally advanced/metastatic disease diagnostic to initiation of larotrectinib (SCOUT) or first line of chemotherapy (external historical control cohort(s)),
 - Intergroup Rhabdomyosarcoma Study (IRS) group,
 - Anatomical site(s) of metastases, if any.
- Collection of treatment-related information:
 - Prior/current surgical treatment(s) for cancer:
 - Anatomical site(s),

⁹ Larotrectinib treatment for the SCOUT study and chemotherapy (first line) for the external historical control cohort(s).

- Date(s) of surgery,
- Best resection (R0, R1, R2),
- Nature of intervention(s) (e.g. amputation or other disfiguring procedures),
- Surgery for a curative intent (excluding amputation) because of the use of systemic treatment.
- Prior/current radiation treatment(s) for cancer:
 - Anatomical sites,
 - Date(s) of radiation therapy.
- Systemic treatment(s), including:
 - Treatment regimen,
 - Date of initiation,
 - Date of radiological or clinical progression,
 - Reasons for discontinuation, as appropriate.

A SLR will be conducted to identify and quantify prognostic factors which could impact the study primary endpoint. This SLR is based on a protocol of research including the following PICO criteria:

- Population: IFS locally advanced or metastatic.
- Intervention: no restriction.
- Comparison: no restriction.
- Outcomes: prognostic factors.
- Type of studies: no restriction except case reports.
- Period: no limit of time.
- Scope: international.

The SLR protocol and report will be annexed to the final study report.

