9.7.7 Complementary analyses

The following complementary analyses will be conducted on the primary, secondary and exploratory endpoints:

- Patients with IFS or other STS with *NTRK* gene fusion.

IFS is a subtype of STS and the most frequent subtype harboring *NTRK* gene fusion. The SCOUT trial included pediatric patients with locally advanced and metastatic STS – other than IFS – harboring an *NTRK* gene fusion, the databases that will be used to constitute the historical external control cohort(s) may also have included such patients. Therefore we propose to analyze IFS patients jointly with other *NTRK* fusion-positive STS. The eligibility criteria for the STS patients for this analysis are detailed below, those for the IFS patients remain unchanged (see [Section 9.2.3.2](#)).

- Inclusion criteria:

The inclusion criteria listed below are in line with those of the SCOUT study in terms of patients and disease characteristics:

- Age \leq 21 years old.
- Locally advanced or metastatic STS.
- Patients with available information on clinical, radiological characteristics of their tumor, therapies administered and outcomes.
- Patients receiving larotrectinib in the SCOUT trial.
- Patients receiving at least chemotherapy-based regimen in the external historical control cohort(s).
- No opposition from the patients and/or representatives for data use.
- Exclusion criteria:
 - Patients treated with TRKi in the external historical control cohort(s).
 - Patients with documented absence of *NTRK* gene fusion.
 - Patients participating in an investigational program with interventions outside of routine clinical practice.

Number of events and censored patients will be reported for all time-to-event endpoints referenced above, and Kaplan-Meier plots of the survival curves will be produced showing median survival and 95% CI, and also survival probabilities at 12 and 24 months.

Frequency tables (n, %) will be produced for discrete endpoints, such as ORR, DCR and incidence rate of treatment discontinuation due to treatment-related AEs.

Additional details on the analyses performed and table shells will be provided in the SAP available as a stand-alone document.

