Larotrectinib is administered as an oral capsule or a liquid formulation at the recommended dose determined in Phase 1 (100 mg/m²; not to exceed 100 mg BID). Cycles are 28 days of continuous BID dosing. Patients undergo periodic radiologic evaluation and ongoing safety assessments as outlined in the protocol. Individual patients will continue daily larotrectinib dosing until PD, unacceptable toxicity, or other reason for treatment discontinuation, as outlined in integrated CSP amendment, version 12.0, section 6.4.

Patients with locally advanced disease and a response of at least a partial response (PR) for a period of one year after PR is initially confirmed may have their larotrectinib treatment withheld, a “wait and see” period, after discussion with the Sponsor. Patients with LGG and a response of stable disease (SD) for a period of at least 2 years after SD is initially confirmed, may similarly have their larotrectinib treatment withheld. Patients in the “wait and see” period will continue to undergo periodic radiologic evaluation and ongoing safety assessments as outlined in section 7.8 of the protocol. If a patient in this “wait and see” period is noted to have evidence of radiographic disease progression, the patient may restart larotrectinib. At the time of larotrectinib re-initiation, the patient will restart all per protocol assessments as delineated for patients on active treatment. Patients who reinitiate larotrectinib treatment are permitted to have their larotrectinib treatment stopped again.

Patients who undergo surgical resection resulting in negative margins may have their study treatment stopped and continue to undergo periodic radiologic evaluation and ongoing safety assessments as outlined in section 7.7 of the protocol. These patients are permitted to restart study treatment, if they experience PD, after discussion with the Sponsor. At the time of larotrectinib re-initiation, the patient will start all assessments per protocol as delineated for patients on active treatment.

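### SAP 6.4 compares stopping for adverse events with no allowance for time on treatment; if larotrectinib is given longer than first-line chemotherapy, its relative risk of discontinuation is overstated.

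*SAP*

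**What the plan says.** Protocol 8.2 lists as a secondary comparison: "Treatment discontinuation rates due to toxicity". SAP 6.4 confines the safety analysis to the incidence of stopping treatment for treatment-emergent adverse events, whether or not related. On the measure it says: "This endpoint will be summarized descriptively by treatment group, with proportions and 95% 2-sided exact binomial confidence intervals", and this is done "in the original unweighted sample only".

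The treatment whose discontinuation is counted is fixed by Protocol 9.3.2 and its footnote 9: larotrectinib in SCOUT, and first-line chemotherapy in the external cohorts.

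On the length of larotrectinib treatment, SAP 3.1.2 says: "Individual patients will continue daily larotrectinib dosing until PD, unacceptable toxicity, or other reason for treatment discontinuation". The same section gives two routes to earlier or temporary stopping. Treatment may be withheld in locally advanced disease once at least a partial response has held for a year from confirmation, and it may be stopped after a resection with negative margins. Restarting is allowed in both cases.

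Neither document states how long first-line chemotherapy lasts, or how long SCOUT patients actually stayed on larotrectinib. SAP 6.2.4 reports duration of follow-up by reverse Kaplan-Meier, which is not time on treatment.

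**The concern.** A patient can be counted as stopping for an adverse event only while on the counted treatment. A control leaves that window when the first-line course is completed or the regimen is changed. A larotrectinib patient who keeps responding and is not resected may stay in it for a year or more. If the two windows differ in length, the proportions reflect that difference as well as how well each treatment is tolerated.

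The study was set up to supply comparative data to a reimbursement authority, and lower toxicity is part of the case made in the protocol's rationale. Without time on treatment in the tables, a reader could not tell a real difference in tolerability from a difference in exposure. Counting events regardless of relatedness adds to the dependence on exposure, because unrelated events also build up with time.

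**Working it through.** The plan gives no figure for this endpoint, so there is none to reproduce.

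**Inputs from the documents**
- Group sizes: 49 SCOUT patients and 42 pooled controls (SAP 4).
- Median time to response on larotrectinib: 1.8 months (Protocol 7.8). Adding the 12 months before response-based withholding gives 1.8 + 12 = 13.8, taken as 14 months. This is an illustration and not a minimum, because resection can end treatment sooner.

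**Assumptions**
- First-line chemotherapy lasts 4 to 12 months.
- Larotrectinib lasts 12 to 36 months.
- The monthly risk of stopping for an adverse event is 0.25% to 2%, equal in both arms unless stated.

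**Constant hazard.** Crude proportion = 1 − exp(−hT), with monthly hazard h and T months on treatment. At h = 1% per month:

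| Larotrectinib vs chemotherapy (months) | Crude proportions | Ratio |
|---|---|---|
| 12 vs 12 | 11.3% vs 11.3% | 1.0 |
| 12 vs 9 | 11.3% vs 8.6% | 1.3 |
| 14 vs 9 | 13.1% vs 8.6% | 1.5 |
| 14 vs 6 | 13.1% vs 5.8% | 2.2 |
| 24 vs 6 | 21.3% vs 5.8% | 3.7 |
| 36 vs 4 | 30.2% vs 3.9% | 7.7 |

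For example, 1 − exp(−0.14) = 13.1% and 1 − exp(−0.06) = 5.8%. The largest ratio in the grid is at 0.25% per month, 36 versus 4 months: [1 − exp(−0.09)] / [1 − exp(−0.01)] = 8.6% / 1.0%, about 8.7 before rounding. The floor of 1.0 arises because the grid never makes larotrectinib the shorter treatment. With 6 versus 9 months at 1% the ratio would be 5.8% / 8.6% = 0.7, so the distortion would run the other way.

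**Front-loaded hazard.** Weibull with shape 0.5 and the same 6-month risk: cumulative hazard = 6h × √(T/6).
- 14 months at h = 1%: 0.06 × √(14/6) = 0.0917, giving 8.8% against 5.8% (ratio 1.5).
- 24 months: 0.06 × 2 = 0.12, giving 11.3% against 5.8% (ratio 1.9).

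**Variable treatment lengths.** With exponential lengths, the proportion is h / (h + 1/mean T). At 1%, means of 24 and 6 months give 19.4% versus 5.7%.

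**Can the order reverse?** Suppose larotrectinib's monthly risk is half that of chemotherapy, 0.5% versus 1%. Over 24 versus 6 months the proportions are 1 − exp(−0.12) = 11.3% and 1 − exp(−0.06) = 5.8%. The better-tolerated treatment shows about twice the proportion.

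**What the added measures recover.** At equal constant risk, a patient-time rate or a cumulative incidence at a common time gives a ratio of 1 (5.8% versus 5.8% at 6 months for 1% per month). A rate alone is not enough if toxicity comes early. In the front-loaded case the average hazard is 0.0917/14 = 0.65 per 100 patient-months for larotrectinib against 0.06/6 = 1.0 for chemotherapy, which now flatters the longer treatment. The common-time estimate avoids this.

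**The case against.** The strongest reply is that the unequal durations are assumed. The documents give neither, and the ratio depends heavily on them. That stands, and the point has to be conditional. A reader might infer from SAP 3.1.2 that larotrectinib is always given until progression, and so certainly accrues more discontinuations than chemotherapy at the same monthly risk. The section does not support that, since it also allows response-based withholding and stopping after a negative-margin resection. Resection matters in this disease: Protocol 7.8 names qualifying for non-mutilating resection as an aim of systemic treatment, and Protocol 7.5.1 records 4 complete surgical responses among 21 SCOUT patients who otherwise faced disfiguring surgery or amputation.

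A reader might also infer a conflict between protocol and SAP, because Protocol 9.7.7 uses the phrase "incidence rate of treatment discontinuation due to treatment-related AEs". The sentence containing it prescribes frequency tables of n and percent, and Protocol 9.1.2 defines the endpoint as an incidence of patients. On the form of the measure, the SAP follows the protocol. Whether related or all adverse events are counted is a separate matter.

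It is also fair that the endpoint is descriptive and untested, so neither alpha nor power is affected. The results are labelled exploratory, and the exact intervals will be wide: 2 of 42 gives 0.6% to 16.2%, and 5 of 49 gives 3.4% to 22.2%. The share of patients who stop for toxicity over treatment as actually given is a legitimate quantity and should stay. None of this makes two proportions over windows of unknown and possibly unequal length a sound comparison of tolerability.

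**Conclusion.** The point holds conditionally. The text establishes that the measure has no time base, that the counted windows are defined differently, and that no output would show whether exposure differed. Whether it did, in which direction and by how much, the documents do not say.

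If larotrectinib exposure is longer, its discontinuation risk relative to chemotherapy is overstated. The size rests on assumed durations and risks: a ratio of 1.0 to about 8.7 at equal monthly risk across the grid, and 1.5 (front-loaded) to 2.2 (constant hazard) for 14 versus 6 months at 1% per month. The plan should be changed because it cannot show which case applies. The added measures favour neither arm in advance.

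**What to change.** In SAP 6.4 keep n (%) with the exact binomial interval, and add for each arm:

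- median time on index treatment, stating whether withheld intervals and restarts count;
- discontinuations for adverse events per 100 patient-months on index treatment, with an exact Poisson 95% confidence interval;
- where stop dates allow, the cumulative incidence at one common pre-specified time, with other ends of treatment (completion, progression, switch, curative resection, death) as competing events.

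The cost is a few table rows. The downside is that stop dates for the control index regimen are not guaranteed. Protocol 9.2.3.1 requires control sources to hold only the date treatment began. Protocol 9.3.4 lists initiation date and reasons for discontinuation for systemic treatment, but no stop date. SAP 6.1.2 lists cycle counts and start/stop dates among baseline items, with the dates for listing only. Some control stop dates may therefore have to be approximated from the number of cycles, and the number approximated should be reported.

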The response endpoints, Overall Response Rate (ORR) and Disease Control Rate (DCR), will be summarized for both groups in both the original and weighted samples.

The binary response outcome is regressed on group indicator (larotrectinib, comparator) using a logistic regression model, incorporating the IPTW weights. Standard errors are calculated using a robust sandwich estimator. The odds ratios comparing larotrectinib to comparator, with 95% confidence interval, will be provided for both ORR and DCR. Odds ratios will also be reported for the unweighted samples.

Incidence of treatment discontinuation due to treatment-related AEs will be summarized descriptively in the original unweighted sampled only.

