SD	Stable Disease
SLR	Systematic Literature Review
SOP	Standard Operating Procedure
STS	Soft Tissue Sarcoma
TLF	Tables, Listings and Figures
TRK	Tropomyosin Receptor Kinase
TRKi	TRK Inhibitor
USA	United States of America
WHO-DD	World Health Organization – Drug Dictionary

1. Introduction

The clinical development program of the first-in-class selective Tropomyosin Receptor Kinase inhibitor (TRKi) larotrectinib, including the pediatric Phase I/II SCOUT study¹, to date has shown that the tumor response observed under treatment with the drug, is pronounced and durable based on results from single arm trials.

In September 2019, larotrectinib was granted a conditional Marketing Authorization (MA) in Europe as monotherapy for the treatment of adult and pediatric patients with solid tumors that display a *NTRK* gene fusion, who have a disease that is locally advanced, metastatic or where surgical resection is likely to result in severe morbidity, and who have no satisfactory treatment options. In France, a dossier was submitted to the National Authority for Health (*Haute Autorité de Santé* [HAS]) in October 2019 to obtain reimbursement of larotrectinib in the country in line with the targeted population described in the MA. In July 2020, the HAS provided positive feedback on the reimbursement of larotrectinib only in pediatric patients with IFS or another STS harboring a *NTRK* gene fusion, which is locally advanced or metastatic, and refractory or in relapse. However, this appraisal is conditional upon the provision of comparative data of larotrectinib treatment *versus* standard of care, in particular in IFS. This study is designed to address this request but also to possibly use the data to provide comparison with historical data as agreed in the pediatric investigation plan (PIP) with European Medicines Agency (EMA).

Given the rarity of the condition and ethics considerations, the use of an external control arm allows for the timely generation of comparative data *versus* SCOUT study data. However, patients who received larotrectinib in the SCOUT trial will likely differ in various underlying characteristics from those who are recorded in the historical control cohorts. This presents a key statistical challenge of adjusting the analysis of primary and secondary endpoints for these patient characteristics in order to avoid biased results.

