1.2 Protocol Version and Amendments

Study 21767/EPI VITRAKVI, v 1.0, 27 JULY 2021.

2. Study Objectives

The primary objective of this study is:

- to compare the time to medical treatment failure (defined as: next systemic treatment or mutilating surgery or radiation therapy or death due to any cause) between larotrectinib and

¹ SCOUT study, a Phase I/II study of the oral tropomyosin receptor kinase (TRK) inhibitor larotrectinib in pediatric patients with advanced solid or primary central nervous system tumors – international clinical study.

standard of care in IFS patients using externally-controlled comparison performed with phase I/II SCOUT study and eligible external historical cohort(s).

The secondary objectives of this study include the comparison of:

- Treatment outcomes (next systemic treatment, mutilating surgery, radiation therapy, death due to any cause),
- Treatment discontinuation rates due to toxicity.

Exploratory endpoints include:

- Progression-free survival (PFS): defined as the time (months) from the start of treatment to the date of first observed disease progression (radiological or clinical, whichever is earlier) or death due to any cause, if death occurs before progression is documented.
- Overall response rate (ORR): defined as the proportion of patients with a best overall response of complete response (CR) or partial response (PR) assessed by investigators.
- Disease control Rate (DCR): defined as the proportion of patients with a best overall response of CR, PR, or Stable Disease (SD).

3. Study Design

This study is a retrospective observational externally-controlled study. Data from patients with IFS within the following the two groups will be compared:

- From the international phase I/II clinical trial called 'SCOUT' conducted in a pediatric population (up to 21 years old) with advanced solid or primary central nervous system (CNS) tumors. Data are collected via electronic case report forms (eCRFs) completed by the investigators during the study conduct in each site.
- External historical control cohorts including:
 - *Institut Curie* database.
 - Database from the *Cooperative Weichteilsarkom Studiengruppe* (CWS, Germany).

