5.1.2 IFS with documented NTRK gene fusion

- Age \leq 21 years old
- Locally advanced or metastatic IFS, which is NTRK fusion-positive.
- Patients receiving
 - larotrectinib in the SCOUT trial, or
 - receiving at least one chemotherapy-based regimen in the external historical control cohorts.

6. Statistical Methodology

A comparison of patients in the larotrectinib group with patients from the external historical control cohorts who received systemic therapy (chemotherapy-based regimen) will be conducted. The external cohorts will comprise a pooled database from the *Institut Curie* and *CWS*.

Patients who received larotrectinib in the SCOUT trial will likely differ in various underlying characteristics from those who are recorded in the historical control cohorts. These characteristics are listed as potential confounders in [section 6.1.2](#). A SLR was conducted to identify key covariates, as described in [section 6.1.3](#). The analyses will need to be adjusted for these patient characteristics to avoid biased results.

The Inverse Probability of Treatment Weighting [IPTW] method will be employed to reduce the effects of measured confounding variables in the interpretation of the treatment effect (larotrectinib *versus* control group). The propensity score (PS) is defined as the probability of a patient receiving larotrectinib conditional on his observed baseline covariates, and is obtained from a logistic regression model. In order to balance the analysis, a weight is assigned to each patient as the inverse probability of being in a certain group conditioning on these baseline covariates. Therefore, for larotrectinib patients, this is the reciprocal of the PS, while for external comparator patients this is the reciprocal of one minus the PS. If a patient has a higher probability of being in a group, it is considered as over-

represented, and therefore is given a lower weight. On the other hand, if the patient has a smaller probability of being in the group, it is considered as under-represented and is given a higher weight. Therefore, the statistical design of this study intends to use this weighting adjustment to remove sampling bias, though diagnostics to check whether balance has been achieved in baseline covariates between larotrectinib and external cohort groups will be performed.

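### Comparing discontinuation due to toxicity is a secondary objective, but SAP 6.4 plans no between-arm estimate and no weighted version, unlike the exploratory ORR and DCR

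*SAP*

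**What the plan says.** SAP section 2 introduces the objective with "The secondary objectives of this study include the comparison of" and lists "Treatment discontinuation rates due to toxicity". Protocol 8.2 does the same ("The secondary objectives in this study include the comparison of"), and Protocol 9.1.2 lists the incidence of such discontinuation among the secondary endpoints.

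On adjustment, SAP section 1 describes as a key statistical challenge "adjusting the analysis of primary and secondary endpoints for these patient characteristics in order to avoid biased results". SAP section 6 repeats the principle: "The analyses will need to be adjusted for these patient characteristics to avoid biased results".

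The planned analysis in SAP 6.4 is: "This endpoint will be summarized descriptively by treatment group, with proportions and 95% 2-sided exact binomial confidence intervals, in the original unweighted sample only". Its closing words, "in the original unweighted sample only", rule out a weighted result. Protocol 9.7.4 had already said this: "Incidence of treatment discontinuation due to treatment-related AEs will be summarized descriptively in the original unweighted sampled only".

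SAP 6.3 carries the weights to the endpoints in 6.3.1 to 6.3.8, which leaves out 6.4. SAP 6.3.7 and 6.3.8 give ORR and DCR exact intervals by group, a weighted odds ratio with a robust sandwich standard error, and an unweighted odds ratio.

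**The concern.** The objective is to compare, but the planned output contains no comparison. A secondary binary endpoint gets less analysis than two exploratory binary endpoints, and neither document gives a reason for the exception to the SAP's own adjustment principle.

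Readers will subtract one crude proportion from the other. That difference has no planned interval, and it mixes treatment with whatever else separates the arms. Line of therapy is one such factor that the SAP itself tabulates. At stake is how the tolerability result is read in a dossier whose stated purpose is comparative evidence.

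**Working it through.** **Figures in the plan.** Neither document gives an expected rate, sample size or power for this endpoint. The nearest stated figure is the primary-endpoint power in SAP section 4. With k = 49/42 = 1.167, m = 49×0.04 + 42×0.19 = 9.94 and a hazard ratio of 0.25, the SAP's formula gives Φ(√(1.167×9.94)×0.75/(1.167×0.25+1) − 1.96) = Φ(0.017) = 50.7%. The SAP states 51%, so its group sizes of 49 and 42 are used below.

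**The binary endpoints side by side.**

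| Endpoint | Status | By-group proportion, exact CI | Unweighted contrast | Weighted contrast |
|---|---|---|---|---|
| ORR, DCR | exploratory | yes | odds ratio | odds ratio, sandwich SE |
| Discontinuation | secondary | yes | none | none |

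**Imbalance on line of therapy.** Inputs from SAP section 7, Table 2: first line 19 of 51 (37.3%) for larotrectinib and 34 of 42 (81.0%) for controls. The larotrectinib counts sum to 51, whereas SAP section 4 gives 49; the documents do not explain this.

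Standardized difference = (0.8095 − 0.3725) / √[(0.3725×0.6275 + 0.8095×0.1905)/2] = 0.4370/0.4404 = 0.99. SAP 6.2.3 takes 10% or below as sufficient balance, so this is about ten times the guideline. For this endpoint the gap may be wider than the table shows. The footnotes to Protocol 9.3.2 and 9.3.4 define the control treatment as first-line chemotherapy, so all controls would be assessed at first line.

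**What that imbalance can do (assumed risks).** Suppose treatment has no effect within line. Let the risk be r1 at first line and r2 at later lines, with all controls assessed at first line. Then:

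crude gap (larotrectinib − control) = (19·r1 + 32·r2)/51 − r1 = (32/51)(r2 − r1)

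| r1 | r2 | Larotrectinib | Control | Spurious gap |
|---|---|---|---|---|
| 2% | 6% | 4.5% | 2% | +2.5 points |
| 3% | 10% | 7.4% | 3% | +4.4 points |
| 5% | 15% | 11.3% | 5% | +6.3 points |
| 10% | 3% | 5.6% | 10% | −4.4 points |

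The sign follows r2 − r1, which the documents do not give.

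**What a contrast adds (assumed counts).** With 2/49 and 5/42, the planned output would be 4.1% (exact 95% CI 0.5 to 14.0) and 11.9% (4.0 to 25.6). The Wilson limits are 1.13% to 13.71% and 5.19% to 25.00%. Newcombe's method then gives:

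- difference = 4.08 − 11.90 = −7.8 points
- lower limit = −7.82 − √[(4.08−1.13)² + (25.00−11.90)²] = −21.2
- upper limit = −7.82 + √[(13.71−4.08)² + (11.90−5.19)²] = +3.9

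Other assumed counts: 1 versus 4 events gives −7.5 (−20.1 to 2.9); 2 versus 4 gives −5.4 (−18.3 to 5.8); 4 versus 4 gives −1.4 (−14.8 to 11.1).

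**Zero events in one arm.** Take 0/49 versus 4/42, unweighted. Every resample of the empty arm is again empty, and its residuals are all zero, so neither a bootstrap nor a sandwich estimator gives that arm any variance. What remains is SE = √(0.0952×0.9048/42) = 0.0453, so the interval is −9.5 ± 1.96×4.53 = −18.4 to −0.6. Newcombe gives −22.1 to −0.3. The first is 17.8 points wide, the second 21.8. A weighted interval built in either way has the same fault. A weighted estimate itself cannot be computed without patient data.

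**The case against.** The strongest reply is that this was deliberate. Descriptive, unweighted reporting is stated in the protocol abstract, Protocol 9.7.4 and SAP 6.4, and Protocol 9.7.3 limits IPTW to time-to-event and response endpoints. That stands: the SAP has not departed from the protocol. But prespecifying the analysis does not make it match the objective, so both documents carry the mismatch.

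A reader might infer that the fault is the absence of a test. The documents do not support that. Both say no formal hypothesis is considered, and the protocol abstract calls the results exploratory. Nor does it follow that the objective is beyond answering: the planned counts are enough for anyone to compute the unweighted difference. What is missing is a prespecified estimate with its interval, and an adjusted one beside it.

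A reader might also cite Protocol Annex 2, Table 4 as showing that tolerability depends on age, a propensity covariate. That table concerns cardiac findings mostly years after anthracycline treatment, not discontinuation on treatment, and Protocol 7.2 names a regimen without an anthracycline as the preferred first line. The line-of-therapy table is the relevant evidence.

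Two further objections hold and limit the remedy. First, the weights rest on survival prognostic factors, clinical judgement and elapsed time, not on determinants of toxicity; in the SLR model, elapsed time stands in for line of therapy. Second, weighting cannot repair differences in how adverse events were recorded, which Protocol 9.9 acknowledges in general terms. The definition also moves, from treatment-related events in Protocol 9.1.2 to treatment-emergent events of any causality in SAP 6.4. SAP section 7 does not list that change, and it needs its own reconciliation.

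**Conclusion.** The point holds as a mismatch between objective and analysis in both documents: a comparison is promised, but neither a between-arm estimate nor a weighted version is planned, while two exploratory endpoints get both. The mismatch and the imbalance (standardized difference about 0.99) come straight from the documents. The effect on the discontinuation result does not: the spurious gaps of 2.5 to 6.3 points rest on assumed risks, and the intervals on assumed counts. Such gaps are modest beside an interval about 25 points wide (−21.2 to +3.9). The documents do not support a claim that the crude comparison favours either arm. This is a worthwhile improvement, not a threat to the study's main conclusion.

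**What to change.** In SAP 6.4:

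- Keep the unweighted proportions and exact intervals.
- Add the unweighted risk difference with a Newcombe 95% interval as the main contrast.
- Add IPTW-weighted proportions and a weighted risk difference, using the weights already computed for the primary endpoint and a robust sandwich standard error, as for ORR and DCR.
- When either arm has zero or very few events, show the weighted difference as a point estimate only and rely on the Newcombe interval. The SAP should fix the number that counts as very few in advance.
- Label both contrasts exploratory. State that the weights may not fully remove the line-of-therapy imbalance and do not address differences in adverse-event ascertainment.

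The cost is a paragraph of SAP text, a few rows in an existing table and a short piece of programming. No new data or weights are needed. If the sponsor prefers to leave the analysis as it is, the minimum is to reword the objective in Protocol 8.2 and SAP section 2 as descriptive, and to justify the exception to the adjustment principle in SAP section 1.
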